PCCI is not surprisingly very difficult to study and is still not well understood including PCCI and MRI changes. We hope that this work including the MRI will add to the knowledge on PCCI but there is no specific MRI "signature". Diagnostic criteria for PCCI has been a topic of recent NIH RFA but it will likely be years before the publications come out from those grants.

2) Purpose

In this pilot study, we propose to test the efficacy of rTMS for the treatment of PCCI. Efficacy measures will include baseline and post-rTMS neuropsychological testing, functional MRI and biometry data using body worn sensors.

3) Lay Summary (approximately 400 words)

Transcranial magnetic stimulation (TMS) is a safe and non-invasive brain stimulation technique. It uses a magnetic coil to stimulate brain tissue painlessly using only a magnet (no electrodes or electrical wires) in a procedure that does not involve any surgery or sedation. TMS is currently FDA approved to treat depression and migraines. Although this technology is applicable to many other brain conditions as well, it has not been systematically examined in individuals with "Chemo-brain". Chemo-brain or Post-Chemotherapy Cognitive Impairment (PCCI) is defined as cognitive changes including impairment of memory, learning, concentration, reasoning, executive function, attention and visuo visio-spatial skills that occur during or after chemotherapy treatment.

In this study, we will:

- 1) use high-resolution magnetic resonance imaging (MRI) of individuals' brains to determine precisely where to place the TMS magnetic coil in order to stimulate the target brain region based off their unique brain structure.
- 2) use TMS to stimulate the target region of the brain.
- 3) take high-resolution MRI pictures of the brain both baseline and post-TMS to study whether the brain activity of the target region changes as a result of the TMS stimulation.
- 4) perform neuropsychological tasks baseline and post-TMS to study if performance is improved following stimulation of the target brain region.
- 5) collect data from completing Frailty assessments, baseline and post-TMS.
- 6) study the short-term and long-term treatment effects.
- 7) collect subject's daily activity and sleep/wake patterns from watch style device (<http://www.actigraphy.com/solutions/actiwatch/actiwatch-plus-specifications.html>).

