- 8) perform behavioral assessments, baseline and post-TMS, to study whether there are measurable changes following stimulation of the target brain region.

4) Resources: Describe the resources (personnel, facilities, time, emergency resources, etc.) available to recruit, consent, conduct study procedures, and analyze data.

Our clinical collaborators will participate in patient recruitment. MRI scans, TMS treatment, neuropsychological assessment, and assessments with body worn devices will be done at the Biosciences Research Laboratories (BSRL) at [name]. All persons assisting with the study have received appropriate training and are or will be knowledgeable in their study-related duties and functions.

[name], Assistant Professor, Cognition and Neural Systems, and her team will be involved in the neuropsychological testing as well as the TMS treatments. Her research focuses primarily on 1) characterizing the mapping between brain organization and behavior, and 2) studies of transcranial magnetic stimulation (TMS) techniques for modulation of human brain function and behavior.

5) Study Population

12 participants with PCCI will be recruited to participate in this trial.

Inclusion Criteria:

- Adult (>=18).
- PCCI diagnosis (see information below).
- Right Handed (We will not enroll left-handed dominant people because they tend to have more symmetric brain function and thus targeting the left frontal region may not be as effective.)
- English speaking.
- Cancer treatment completed and considered curative with the exception of endocrine therapy after chemotherapy.
- Able to attend daily intervention (Monday-Friday) for 2 weeks.
- Not enrolled in another interventional study within 6 months prior to beginning this study.

Exclusion Criteria:

- Pregnancy or thinking of becoming pregnant.
- Undergoing active treatment for cancer.
- Routine contraindications for MRI (including incompatible medical implants or metal fragments in the body at risk for migration or heating with application of the magnetic field) including severe claustrophobia.
- History of brain metastasis or other brain tumor.
- History of stroke or traumatic brain injury.
- Frequent or severe headaches.
- Cognitive or mood disorder prior to chemotherapy (i.e. dementia or depression).
- History of epilepsy, or other seizure disorders.
- History mental health disorders, such as substance misuse, bipolar disorder or psychosis.

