A selection of the following memory tasks, which include Face Name Associative Memory Exam, Memory Capacity Test, Short-Term Memory Binding test, Behavioral Pattern Separation-Object test, Spatial Pattern Separation task, Discrimination and Transfer task, Dual tasking task, and other similar memory tasks (Rentz et al.), will be used to assess memory function. These memory tasks contain various shapes, colors, numbers, letters, objects, background (e.g., environments in our daily life), names, occupation titles, and ordinary faces. The memory task will require approximately 30 minutes.

D) Frailty assessment (see attached document: Frailty Meter device manual BioSensics.pdf)

Frailty will be assessed by measuring motion of forearm and upper-arm via wearable motion sensors attached to the upper extremity (tri-axial wearable gyroscope sensor, BioSensics LLC, Cambridge, MA). Participants will perform fully elbow flexion and extension with their dominant arm repetitively and as quickly as they can within 20 seconds. Motion score will be estimated with the following variables: (a) speed; (b) flexibility; (c) power; (d) rise time; (e) moment; (f) speed variability; (g) speed reduction, (h) flexion number, (i) BMI; and (j) Age. The

whole assessment will take around 10 minutes to complete. This will be done pre and post treatment.

E) TMS treatment

The purpose of the study is to test the acceptability and practicality of rTMS for the treatment of PCCI. Efficacy measures will include baseline and post-rTMS neuropsychological testing, functional MRI and biometry data using body worn sensors. All study activities will occur at the Biosciences Research Laboratories (BRS) Building, located at [name].

Theta burst stimulation (TBS) is a safe and patterned repetitive TMS protocol. In this project, we will apply the intermittent TBS (iTBS) protocol at the left dorsolateral prefrontal cortex. The iTBS paradigm consists of 3 pulses of 50 Hz stimulation repeated at 200-ms interval (i.e., 5 Hz) for 2 seconds (30 stimuli for 2 seconds). The 2-second train of stimulation will repeat every 10 seconds for 190 seconds (600 stimuli in total). A single session of iTBS induces transient effects on the targeted brain structures/networks that tend to last approximately 60 minutes following a single application. Structural MRI for TMS target localization and baseline functional MRI (fMRI) will be performed.

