After the conclusion of baseline data acquisition, the research team will analyze each participant's unique structural and functional connectivity patterns to determine stimulation site for TMS in future study sessions.

The subjects will receive 10-sessions (1 session per day, M-F over 2 consecutive weeks). The treatment itself lasts approximately only 190 seconds but we are conservatively planning an hour slot in order to not rush the daily planning/positioning.

After the last rTMS session, follow-up neuropsychological testing, behavioral assessments, and fMRI will be performed.

At 30, 90 and 120 days post the last rTMS session, a selection of neuropsychological and behavioral assessments will be mailed to the patients for the subject to complete and mail back. These assessments may be done alternatively over the phone.

F) Actiwatch

Data will be collected using Actiwatch spectrum plus (hardware) over a period of up to 2 weeks from our subjects. This data will be stored in a computer and processed using Actigraph (software licensed from Philips Respironics). The equipment is off the shelf commercial products with FDA approvals.

The subject will wear Actiwatch on their wrist and perform regular activities: sleeping, sitting, running, walking, etc. After finishing data collection, the Actiwatch will be returned to the study staff. The study staff will use USB cord to download the data to computer with actigraph software. This assessment is optional.

G) Behavioral Assessments

A selection of the following assessments may be performed, either on paper, electronically or over the phone. Assessments include PRO-CTCAE and the PSQI Sleep Questionnaire. See details in file "Behavioral assessments.pdf". These assessments will require approximately 30-60 minutes.

9) Cost to Subjects

There is no monetary or financial cost incurred by participants who enroll in this trial. Participants will, however, be responsible for their own travel to the research laboratory. While the participants will not be reimbursed for travel, the research team will cover the cost of parking.

Though no other monetary/financial costs are affixed with participation in this trial, there is a **significant “time cost”** associated with completing this trial. Given the nature of this trial, we understand that this may place a burden on the participant's scheduling and whereabouts.

10) Risks to Subjects

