- All paper information will be kept under double lock and key in the coordinator's office. Only key personnel will have access to this data.
- Digital records will be stored in password protected files, on university maintained servers that undergo regular and secured back-up. Any sensitive data will be encrypted.
- All laboratory computers will be protected with a sign-in password.
- Any data shared with collaborators will be de-identified.
- No data will be shared with collaborators without the approval of an additional IRB amendment.
- Pursuant of University guidelines, research records will be stored for six years after the completion of the research.
- A key limitation of this agreement would arise in the event of an audit.
 - If the study is randomly chosen to be audited, regulatory officials would have access to all study records. This is the only instance in which non-key personnel would have access to data collected in this study.

14) Subject Compensation

Participants will not be compensated for being a part of this feasibility study.

15) Withdrawal of Subjects

Participants can be withdrawn from the study at any time with no penalty. The participants can prompt this withdrawal themselves if they no longer wish to continue with the trial or their participation in the study can be terminated by the research investigators for any reason. Participants will be informed of this during the consent process. This arrangement for withdrawal without penalty will promote participant safety and the accuracy of the data collected by the investigator.

In the event of participant withdrawal: 1) participants will be asked whether they are willing to complete the follow-up testing and surveys, and 2) the research team will thoroughly document the event. In cases that abrupt withdrawal is necessary, participant safety will remain our ultimate goal and we will follow protocols to ensure participants are not put at increased risk.

16) Sharing of Results with Subjects

Results will not be shared with research participants. However, exceptions may be made with raw MRI image file if research participants specifically request a picture of their brain as study memento.

17) Clinical Trials.gov Information

Registration pending

18) Statistical Analysis Plan

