Repeated measures ANOVA will be employed. The independent variable is rTMS treatment. The primary outcome measure is cognitive function, and the secondary outcome measures is brain functional connectivity. Alpha = 0.05 will be used as the significance level for all analyses. Results will be corrected for multiple comparisons.

19) SCHEDULE OF EVENTS

Study stage	Baseline	Treatment Week #1		Treatment Week #2	Final Treatment	Follow-Up		
		Day 1	Day 2-5			Day 42 +/- 7	Day 102 +/- 25	Day 132 +/- 25
Study event	Day 0				Day 12			
Consent	X							
Neuropsychological testing	X				X	X	X	X
Behavioral testing	X				X	X	X	X
Urine Pregnancy test	X							
Structural MRI	X							
Functional MRI	X				X			
TMS treatment*		X	X	X	X			
Actiwatch ¹		X	X	X	X			
Frailty task		X			X			

*The TMS treatment sessions do not need to start immediately after Baseline.
¹Optional tasks, subjects can opt out this task.

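### With one treated group and no comparator, the Section 18 treatment factor cannot be separated from time, so the ANOVA measures within-subject change and cannot test rTMS efficacy

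*Combined protocol and SAP*

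**What the plan says.** Section 5 describes one group: "12 participants with PCCI will be recruited to participate in this trial". Section 8E gives everyone the same course: "The subjects will receive 10-sessions (1 session per day, M-F over 2 consecutive weeks". Intermittent theta burst stimulation of the left dorsolateral prefrontal cortex is the only condition. The one sham control mentioned, in Section 1, belongs to an earlier depression trial, and the randomised codes in Section 12 are for de-identification.

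The purpose is stated in three ways:

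- Section 2: "we propose to test the efficacy of rTMS for the treatment of PCCI".
- Section 8E: "The purpose of the study is to test the acceptability and practicality of rTMS for the treatment of PCCI". The next sentence, as in Section 2, reads "Efficacy measures will include baseline and post-rTMS neuropsychological testing, functional MRI and biometry data using body worn sensors".
- Section 14: "Participants will not be compensated for being a part of this feasibility study".

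Section 18 specifies a repeated measures ANOVA at alpha 0.05 with correction for multiple comparisons. Of the model it says only "The independent variable is rTMS treatment". It does not define levels or name time as a factor. On outcomes, "The primary outcome measure is cognitive function", with brain functional connectivity as secondary. It contains no analysis of acceptability or practicality. Section 19 schedules neuropsychological testing at baseline (Day 0), Day 12 and three follow-ups. Under Section 8E the follow-ups use a selection of the tests, by post or telephone.

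**The concern.** A reader who puts Sections 2 and 18 together would take a significant F test as evidence that rTMS works. With one treated group, anything else that changes between baseline and Day 12 moves the same contrast. For cognitive tests the obvious candidate is practice, because the same subjects are tested again about two weeks later. Natural recovery is another: Section 1 says the condition can be transient, and the footnote to Section 19 leaves the gap between baseline and first treatment open. Expectation is a third, since every subject knows that they are treated. Practice mainly affects the cognitive outcome, but the confounding with time applies to functional connectivity as well.

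What is at stake is the conclusion the trial may draw. The documents state two different purposes. The analysis cannot deliver the one in Section 2 and does not address the one in Section 8E.

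**Working it through.** The plan gives no power, effect size, SD or sample-size calculation, so there is no stated figure to reproduce. The check has two parts: what the model can estimate, and how far a time effect alone could move the test.

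**1. What the factor can estimate.** Inputs from the documents: 12 subjects (Section 5), five cognitive testing times (Section 19), all subjects treated (Section 8E). The design matrix has 12 × 5 = 60 rows.

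| Terms in model | Rank | df added |
|---|---|---|
| Subject | 12 | – |
| Subject + treatment as an arm factor | 12 | 0 |
| Subject + before/after treatment | 13 | 1 |
| Subject + time (5 levels) | 16 | 4 |
| Subject + time + before/after treatment | 16 | 0 beyond time |

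As an arm factor, treatment has no degrees of freedom. As a before/after factor it has one and the ANOVA can be run, but it adds nothing once time is in the model: it is fully aliased with time. With only baseline and Day 12, the two factors are the same column.

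**2. Size of the problem, illustrated.** A two-level within-subject ANOVA is a paired t-test (F = t²) with 12 − 1 = 11 df. The two-sided 0.05 critical value is 2.201. From the documents: n = 12 and alpha = 0.05. Assumed, because the documents give neither: retest reliability r from 0.6 to 0.9, and a practice gain g of 0.1 or 0.2 SD on a single test. The true rTMS effect is set to zero. A two-sided test and complete data on all 12 are also assumed.

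- SD of change = √(2(1 − r)): √0.8 = 0.894 at r = 0.6; √0.2 = 0.447 at r = 0.9.
- Noncentrality = (g / SD of change) × √12.

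| g | r | g / SD of change | Noncentrality | Rejection at 0.05 |
|---|---|---|---|---|
| 0.1 | 0.6 | 0.112 | 0.387 | 6.5% |
| 0.1 | 0.9 | 0.224 | 0.775 | 10.9% |
| 0.2 | 0.6 | 0.224 | 0.775 | 10.9% |
| 0.2 | 0.9 | 0.447 | 1.549 | 29.3% |

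So the rate runs from about 6.5% to 29% where 5% is intended.

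**3. Does the multiplicity correction help?** Section 18 names neither the method nor the number of comparisons, so take 0.005 as an assumed corrected level. With a gain of 0.2 SD, rejection is 1.6% (r = 0.6) to 6.5% (r = 0.9), which is 1.6/0.5 = 3.2 to 6.5/0.5 = 13 times nominal. The correction lowers the absolute rate, but it controls chance error and leaves the shift in the mean where it was.

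**The case against.** The strongest reply is that the plan is a coherent pre-post pilot. In a repeated measures ANOVA the natural reading of the factor is before versus after rTMS, and exposure does differ within each subject: none at baseline, ten sessions by Day 12. This stands. A reader might infer that the factor has only one level and that the analysis cannot be run. The documents do not support that, and renaming the factor time leaves the F statistic unchanged. What changes is what the F test may be said to show.

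Secondly, the documents already temper the claim. Section 2 calls the study a pilot, Section 8E speaks of acceptability and practicality, Section 14 of feasibility, and Section 11 expects no direct benefit to participants. No passage says how a significant result will be reported, so a misleading report is an inference. This also stands, and a single arm of 12 is a legitimate pilot design. But these statements do not cancel the efficacy aim in Section 2; they contradict it. Measuring efficacy by baseline and post-treatment scores does not make the change attributable to rTMS.

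Thirdly, the rejection rates depend on assumed values, and at the lower end they barely exceed 5%. That is true. The aliasing needs none of those values.

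**Conclusion.** The concern holds in this form: treatment and time are fully confounded, so the Section 18 analysis estimates uncontrolled within-subject change and cannot test the efficacy aim in Section 2. That follows from the design alone. The range of 6.5% to 29% illustrates practice on one test under the stated reliabilities and gains. Natural recovery and expectation are not quantified, because the documents give no basis for a size.

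Two stronger readings should not be drawn. The first is that the trial is invalid without a control arm: nothing in the feasibility purpose requires one. The second is that regression to the mean is known to be a large extra bias. Sections 5 and 6 do select on low scores at the first appointment, and this may push change upwards if that visit is also the Day 0 baseline. That identity is inferred from the consent rule and the single baseline column in Section 19. The size also depends on how many memory tasks count towards eligibility, which Section 5 does not say; the attached files named in Section 8 were not available and may say. In simulations with an assumed referral mean at the norm, reliability 0.6, true-score correlation 0.6 and independent errors, rejection fell from roughly 70% with two tests to a little over 10% with eight. No conclusion here rests on it.

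**What to change.** 1. **Section 18.** Name time as the within-subject factor, with baseline versus Day 12 as the main contrast. Treat the posted or telephone follow-ups as secondary, because they differ in mode and use only some of the tests. State that a significant result is uncontrolled within-subject change and not evidence of rTMS efficacy.
2. **Sections 2, 8E and 14.** Reconcile the purpose; which one applies is for the investigator to decide. Under either, replace the efficacy wording in Sections 2 and 8E with terms a single-arm design supports, such as exploratory within-subject change.
3. **If acceptability and practicality is kept as the purpose,** add a descriptive analysis to Section 18: sessions attended out of 10, and completers out of all who start, with an exact confidence interval. Without it, the stated purpose has no analysis.

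The first two are wording changes, and the third uses data that should be logged routinely. The real cost is giving up the efficacy claim. No control arm, added subjects or added visits are needed. Repeating a few named cognitive tests on Day 1 before the first session, as a second baseline, is optional: it would lengthen that visit and add a practice exposure, and it would not remove continuing practice or recovery.

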Appendix 1: Data and Safety Monitoring Plan:

1. Identification of the DSMB obligated for oversight responsibilities:

The University of Arizona Cancer Center Data and Safety Monitoring Board (DSMB) will provide ongoing oversight for this trial. This study has been assigned a Medium Risk level by the DSMB.

2. Identification of the entity obligated for routine monitoring duties:

Routine monitoring will be provided by the Quality Assurance/Quality Control (QA/QC) Program to ensure that the investigation is conducted according to protocol design and regulatory requirements.

This trial will also undergo real-time monitoring by the PI and study team, including documentation of real-time monitoring of any new or ongoing safety issues.

The trial will have a AE/SAE log that will be reviewed and signed by the PI in a timely manner of the knowledge and documentation of the occurrence of an AE/SAE. SAEs will be reviewed within 24 hours of notification of event.

3. Monitoring progress and data review process:

Routine monitoring of subject data will be conducted at least quarterly.

The first routine monitoring visit will include at a minimum:

- Informed consent – 100% of cases enrolled;
- Subject eligibility – 50% of cases, up to two subjects;
- Data review – 50% of cases, up to two subjects.

All subsequent monitoring visits will consist of randomly selected subject cases based on current enrollment and include continuing review of previously selected cases, as applicable.

A monitoring visit report and follow-up letter will be completed approximately two weeks after the routine monitoring visit; a copy will be maintained in the study file. The monitor will request additional source documentation, clarification, information, or corrections to the CRF and/or regulatory records from the Clinical Research Coordinator (CRC) or other applicable staff responsible for the study and resolution of queries/findings. Documentation of such a request will be maintained with a copy of the monitor's visit report for follow-up at the next monitoring visit. Electronic records will be available in the institutional database or provided by the QA/QC Program staff.

The Principal Investigator will ensure the accuracy, completeness, legibility and timeliness of the data reported in the Case Report Form (CRF). Source documentation

supporting the study data should indicate the subject's participation in the trial and should document the dates and details of study procedures, adverse events, and patient status.

Case report forms will be created to include study data points and the adverse event forms and be completed using the institution database or other acceptable data formats. All subject forms and study files will be stored in a secure area limited to authorized staff.

Note: Routine monitoring of regulatory documents and test article will be conducted at least annually.

4. Process to implement study closure when significant risks or benefits are identified:

We do not anticipate any additional significant risks or benefits associated with the research. If there is a reason to close the study before the planned study end, there are no additional risks to the subjects for sudden withdrawal.

This research is not part of the subject's standard of care so if the study ends early, there would be no continuing interaction with the subject in the event we closed the study due to any newly identified significant information.

5. Description of adverse events and reporting procedures:

ADVERSE EVENTS

An adverse event (AE) is any untoward medical occurrence in a patient or clinical investigation subject administered a pharmaceutical product and that does not necessarily have a causal relationship with this treatment. An AE can therefore be any unfavorable and unintended sign, symptom, or disease temporally associated with the use of a medicinal (investigational) product, whether or not related to the medicinal (investigational) product.

Any and all adverse events will be recorded on the UACC adverse events record form and reviewed by the Principal Investigator.

All adverse events will be classified using either the MedDRA term or NCI Common Terminology Criteria for Adverse Events (CTCAE) version 4.0 and will address:

- Grade
- Relationship to study drug (not related, unlikely, possible, probable, definitely)
- Causality other than study drug (disease related, concomitant medication related, intercurrent illness, other)
- Date of onset, date of resolution
- Frequency of event (single, intermittent, continuous)
- Event outcome (resolved, ongoing, death)
- Action taken (none, held, dose reduced, discontinued, medication given)

SERIOUS ADVERSE EVENTS

A serious adverse event (SAE) is any untoward medical occurrence that at any dose:

- 1) Results in death;
- 2) Is life-threatening;
- 3) Requires in-patient hospitalization or prolongation of an existing hospital stay;
- 4) Results in disability persistent or significant disability/incapacity, or;
- 5) Is a congenital anomaly/birth defect.

Note: A SAE may also be an important medical event, in the view of the investigator that requires medical or surgical intervention to prevent one of the outcomes listed above.

All serious adverse events, regardless of attribution, and any deaths will be reported within 24 hours of notification of the event to the sponsor and, if applicable, any collaborating entity. All serious adverse events and any deaths will be reported to the DSMB and to the University of Arizona Human Subjects Protection Program per the guidelines set forth in University of Arizona Cancer Center Data and Safety Monitoring Board Charter, Table 5: Adverse Event Reporting.

All submitted serious adverse events will be processed by the DSMB Coordinator monthly for initial trend analysis and then reviewed by the DSMB Chair. The assigned QA/QC Monitor will review the SAE reporting process to confirm reporting requirements are met.

6. Plan for assuring data accuracy and protocol compliance:

Routine study activity and safety information will be reported to the DSMB quarterly, or more frequently if requested. These reports will include:

- Study activity, cumulative and for the period under review;
- Safety (narrative description on non-serious and serious adverse events, protocol pre-determined early stopping rules for safety or treatment-emergent adverse events);
- Predetermined protocol early stopping rules for efficacy/futility;
- Status of study in relationship to stopping rules;
- Current dose level of study agent;
- Routine monitoring and protocol compliance (describe the monitoring process and identify the status of the monitoring);
- Comments;
- Attachments (AE data reviewed by the PI to compile the report, SAE letters and reports, results of any review(s), applicable correspondence with the IRB or other regulatory agencies

Data, safety and study progress will be reported to:

- Human Subjects Protection Program (IRB) at least annually;
- Sponsor (if applicable) at least every six months.

7. Identification of the sponsor or funding agency, as applicable:

The PI will immediately notify, in writing, the funding agency, if applicable, any action resulting in a temporary or permanent suspension of the study.

A copy of this correspondence will also be forwarded to the DSMB and the SRC.

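### Appendix 1 attributes adverse events to a drug that nobody receives, and the schedule has no adverse-event check at any iTBS session, so relationship to rTMS and mild, transient events are weakly captured

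*Combined protocol and SAP*

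**What the plan says.** **Intervention.** Section 8E states that "we will apply the intermittent TBS (iTBS) protocol at the left dorsolateral prefrontal cortex". On dosing frequency it says "The subjects will receive 10-sessions (1 session per day, M-F over 2 consecutive weeks". Section 5 gives the sample: "12 participants with PCCI will be recruited to participate in this trial". The protocol describes no study drug and no sham or control group.

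**Purpose.** Section 8E also says: "The purpose of the study is to test the acceptability and practicality of rTMS for the treatment of PCCI".

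**Definition and attribution.** Appendix 1, item 5, opens: "An adverse event (AE) is any untoward medical occurrence in a patient or clinical investigation subject administered a pharmaceutical product". Its second sentence ties an event to the use of a medicinal product. Each event is then given a "Relationship to study drug (not related, unlikely, possible, probable, definitely" grade. A further field covers causes other than the study drug, with four categories: disease, concomitant medication, intercurrent illness and other. The action field includes a dose reduction, and item 6 asks for the current dose level of an agent in the DSMB reports. None of these fields names rTMS, the device or a study procedure.

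**Ascertainment.** The Schedule of Events (Section 19) has no row for adverse events, safety or tolerability. Behavioral testing is marked at Baseline (Day 0), at the final treatment (Day 12) and at the three follow-ups. Section 8G lists PRO-CTCAE within that testing, under the wording "A selection of the following assessments may be performed, either on paper, electronically or over the phone".

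**Safeguards.** Item 5 requires every adverse event to be recorded, reviewed by the principal investigator, and classified by MedDRA or CTCAE version 4.0, with grade, dates, frequency and outcome. Item 2 provides an AE/SAE log and real-time safety monitoring. Serious events are reported whatever their attribution.

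**The concern.** Two separate steps produce a usable count of treatment-related events: someone has to find the event, and someone has to judge whether the treatment caused it. The plan is weak at both.

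On judgement, the causality question concerns something no participant receives. One rater may take the study drug to mean iTBS. Another may answer the question as printed and mark the event unrelated. There is no comparator arm whose background event rate could be subtracted, so the relationship field is the main planned route to a count of rTMS-related events.

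On finding events, mild and transient symptoms after stimulation are the ones most easily lost without a standing question, and they are the ones that inform acceptability. Section 10 itself discusses seizure as a risk of repetitive TMS, and Appendix 1 records a Medium Risk assignment by the DSMB. The quarterly DSMB reports draw on these same data.

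**Working it through.** The plan gives no figure on this point to reproduce. The check is a comparison of passages and a count.

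**1. Intervention against the safety fields**

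| Item in Appendix 1 | What it refers to | Counterpart in this trial |
|---|---|---|
| AE definition, first sentence (item 5) | a pharmaceutical product | none |
| AE definition, second sentence (item 5) | a medicinal product | none |
| Relationship grade (item 5) | study drug | none |
| Other causality (item 5) | anything except study drug | iTBS fits only under other |
| Action taken (item 5) | includes a dose reduction | no meaning stated for iTBS |
| DSMB report (item 6) | dose level of an agent | no meaning stated for iTBS |

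**2. One event passed through the fields**

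Take a short headache after the third session.

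- Literal reading: no drug was given, so the relationship is graded as unrelated. The other-cause field has disease, concomitant medication, intercurrent illness and other, so the event is coded as other.
- Reading with iTBS substituted for the drug: the relationship may be graded possible, probable or definite.

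The same event can thus be counted as treatment-related or not, depending on which reading the rater adopts. The text does not choose between them.

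**3. Sessions with a scheduled symptom inquiry**

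Inputs: 12 subjects (Section 5); 10 sessions each (Section 8E); behavioral testing at Day 0, Day 12 and three follow-ups (Section 19).

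- Planned sessions: 12 × 10 = 120.
- Weekday sessions over two consecutive weeks starting on Day 1 fall on Days 1–5 and 8–12, so Day 12 is the tenth session.
- Day 0 precedes treatment and the follow-ups come after it. Behavioral testing therefore coincides with a session on one day only, Day 12.
- If PRO-CTCAE is used on Day 12: 10 − 1 = 9 sessions per subject without a scheduled symptom inquiry; 9 × 12 = 108; 108 / 120 = 90%.
- If PRO-CTCAE is not among the assessments selected that day: 10 × 12 = 120 of 120.

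The range is 108 to 120 of 120 sessions, assuming that all 12 subjects complete all 10 sessions. A dedicated adverse-event check is scheduled at none of them.

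**4. What the safeguards cover**

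The recording, grading, log and review rules govern an event once it is known. Real-time monitoring is required, but no question, time point or responsible person is given for each session. Serious-event reporting does not depend on the relationship field, so the mislabelled field does not hold up those reports. What remains is the non-serious event that nobody is scheduled to ask about.

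**The case against.** The strongest reply is that this is leftover template wording which nobody would apply literally. With a single intervention, staff would naturally read the study drug as iTBS; item 5 also speaks of a treatment, and item 3 of a test article. A fully literal reading would leave no adverse events to record, yet Appendix 1 requires a log for this trial. Staff are with the subject at each session. The institutional adverse-event form and the behavioral assessment file are not in the documents and may be better worded. The SAP (Section 18) makes cognitive function primary and functional connectivity secondary, and has no tolerability endpoint, so no planned analysis changes.

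Much of this stands, and it rules out several stronger readings that a reader might infer:

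- *That rTMS-related events go unclassified.* Item 5 has all events coded and graded.
- *That no rate of rTMS-related events can be reported.* Staff could reinterpret the field, and onset dates set against session dates would permit a rate of events after treatment.
- *That early events are found only if the subject volunteers them.* The documents do not say how events are elicited. A missing schedule row shows that no inquiry is scheduled, not that none is made.
- *That 108 sessions' worth of events are missed.* The figure counts sessions without a scheduled instrument. The documents also do not give the recall period of PRO-CTCAE, so a Day 12 questionnaire might reach back to earlier sessions.

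What the reply does not remove is that the operative text must be reinterpreted before it yields an attribution to rTMS, and that it sets no common reinterpretation. Nor does it supply a per-session procedure. Section 2 states an efficacy purpose, but that does not cancel the acceptability purpose in Section 8E.

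**Conclusion.** The concern holds in a limited form. The definition, relationship, action and DSMB-report items are written for a drug, so relationship to rTMS has no valid field. The schedule contains no adverse-event check at any of the 10 sessions, and at least 108 of 120 planned sessions (90%) have no scheduled symptom inquiry. That count rests on full enrolment and attendance, and it gives the plan the benefit of PRO-CTCAE on Day 12.

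The effect on the reported event rate cannot be sized from the documents. Under-ascertainment would tend to make the course look better tolerated than it is, but neither its extent nor its occurrence is shown. Serious-event reporting and the efficacy analysis are unaffected. The correction should be made because it is cheap and bears on a stated purpose, and because a mild event not asked about at the time may not be recoverable later.

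**What to change.** - **Appendix 1, item 5:** replace the drug terms in the adverse-event definition and in both causality fields with *study intervention (iTBS) or study procedure*. Reconcile the action field with the intervention actually given.
- **Appendix 1, item 6:** replace the dose-level entry in the DSMB report with the number of sessions delivered.
- **Section 19:** add an adverse-event row marked at each treatment session, with one standard open question, the answer recorded against the session number.
- **Section 18:** state that iTBS-related events will be reported per subject and per session, with 12 and 120 as the planned denominators and the numbers actually treated and delivered as the reported ones.

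Separate attribution to MRI is optional and not needed for this correction.

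The cost is a wording change, one case report form line per session and a few minutes of staff time. Section 8E already sets aside an hour for a stimulation of about 190 seconds. The downside is a possibly higher reported event count, since a standing question tends to find more than an unprompted log.
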